We will assess this hypothesis in the context of a two factor repeated measures mixed model ANOVA, with one between subjects factor with two levels (pregnenolone vs. placebo) and one within subjects factor with three levels (Weeks 0, 4, 8 of treatment post-randomization, which correspond to Visits 2, 4, and 6). This hypothesis will be tested using the treatment-by-time interaction, followed by contrasts in least squares means. These contrasts will examine the difference between the treatments at Weeks 4 and 8 on the changes between least squares means between Week 0 to Week 4, and Week 0 to Week 8 of treatment post-randomization. We will perform several such analyses, one for functional outcome as assessed by the Physical Component of the SF-36 (primary endpoint), and others for secondary endpoints, including: pain symptoms (as assessed by the Brief Pain Inventory), executive functioning (as assessed by the Tower of London test of the BACS), fatigue (as assessed by the Multidimensional Fatigue Inventory), and overall psychological functioning (as assessed by the Global Severity Index of the SCL-90R). The response variable will be change from baseline, and we will use baseline as a covariate. Exploratory outcomes will include the BACS composite score (cognitive symptoms), resilience (as assessed by the Connor-Davidson Resilience Scale), anxiety and depression symptoms (as assessed by the Hospital Anxiety and Depression Scale), PTSD symptoms (as assessed by the PTSD Symptom Checklist), and depression symptoms (as assessed by the Beck Depression Inventory-II scale).

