For the purpose of power calculations we assume that the mean pain levels of the two independent groups will be compared using a Two-Sample T-Test, Null Hypothesis: Mean1=Mean2. Alternative Hypothesis: Mean1 > Mean2. The standard deviations were assumed to be unknown and equal.

Assuming specified numbers of participants in each group (N) the mean differences detectable for at least 80% power and alpha=0.05 are shown in the following table and figure.

N1	Mean1	Mean2
4	6.0	3.6
5	6.0	3.8
6	6.0	4.0
6	6.0	4.2
8	6.0	4.4
10	6.0	4.6
12	6.0	4.8
17	6.0	5.0
26	6.0	5.2
45	6.0	5.4
100	6.0	5.6

Group sample sizes of 45 achieve at least 80% power to detect a difference of 0.6 between the null hypothesis that both group means are 6.0 and the alternative hypothesis that the mean of group 2 is 5.4 with estimated group standard deviations of 1.0 and 1.0 and with a significance level (alpha) of 0.05 using a two-sided two-sample t-test. We will have 70 Veterans per group, and should thus have **94% power to detect a difference in pain symptoms of 0.6** in the pregnenolone intervention compared to placebo.

POWER ANALYSIS: COGNITIVE SYMPTOMS (Secondary Endpoint)

Executive functioning as assessed by the Tower of London Test of the BACS cognitive assessment battery, Keefe et al.

The Tower of London component of the BACS cognitive assessment battery demonstrated improvements in the hypothesized direction in two of our prior pilot RCTs in Veterans with schizophrenia and mild TBI who had been randomized to pregnenolone (moderate effect sizes). We thus did power and sample size calculations for Tower of London executive functioning scores (secondary cognitive outcome measure) from estimates of means and standard deviations (SD) from preliminary data derived from our pilot RCT examining pregnenolone in OEF/OIF era Veterans with mild TBI. We conservatively utilized our pilot RCT in Veterans with TBI rather than our pilot RCT in Veterans with schizophrenia, as Veterans with schizophrenia demonstrated somewhat greater mean improvements in the Tower of London test (z-score change 0.61 greater than placebo). We used simplified models on change scores for power calculations as we do not know, and cannot reasonably estimate, the covariance parameters we would need to do these calculations in the context of the mixed models. We used correlations of 0.50 between all occasions, which is probably a conservative estimate (please see attached scoring information for BACS in Appendix).

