Preliminary Exploration: We will explore the data using descriptive statistics and graphical techniques prior to any hypothesis testing. For categorical variables, we will examine frequency distributions and where appropriate contingency tables and histograms. For continuous variables, we will examine frequency distributions and where appropriate stem-and-leaf plots and box-and-whisker plots. When appropriate, we will consider transformation. If

necessary, due to distributional considerations, we will consider a change of analysis method to a less parametric one. For time-to-event variables, we will use Kaplan-Meier plots to obtain a global picture of the patterns in each of the treatment groups.

General Modeling: Most of our hypotheses specify continuous response variables assessed longitudinally. For those models, we will use mixed models repeated measures models. There are three assessment points for the primary and secondary outcome measures (to be administered at Visits 2, 4, and 6; each study visit is two weeks apart). We will use an AR(1) covariance structure for the repeated measures. We will fit the models preliminarily using AR(1) covariance structures and using unstructured covariance structures, and use the difference between the two -2 log likelihood functions to construct a likelihood ratio test of the advantage of the unstructured covariance structure. If the unstructured covariance structure does not fit significantly better, we will use an AR(1) structure.

We will examine group differences in least squares means at each of the major time points (Weeks 0, 4, 8 of treatment post-randomization) as described in the plans for specific hypotheses. Distributional assumptions will be examined using residuals. We recognize that it is always possible that these mixed models may fail to converge or encounter difficulties based on their use of asymptotics. In that case, we will move to analyses that assume compound symmetry, and use a Huynh-Feldt correction for the extent to which compound symmetry fails to be met.

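### AR(1) covariance is kept unless a likelihood ratio test rejects it; when moderate misfit is missed, standard errors can be off in either direction, and unstructured covariance would avoid this at almost no cost

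*Combined protocol and SAP*

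**What the plan says.** General Modeling in the Statistical Analysis Plan sets the default: "We will use an AR(1) covariance structure for the repeated measures". Both structures are fitted, and the plan will "use the difference between the two -2 log likelihood functions to construct a likelihood ratio test of the advantage of the unstructured covariance structure". The rule ends: "If the unstructured covariance structure does not fit significantly better, we will use an AR(1) structure". No test level, degrees-of-freedom method or robust standard error is named. If a model does not converge, the fallback is compound symmetry with a Huynh-Feldt correction.

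The size of the covariance matrix is not settled. General Modeling says "There are three assessment points for the primary and secondary outcome measures". The Primary Outcome text under Study Interventions describes "one within subjects factor with three levels (Weeks 0, 4, 8 of treatment post-randomization", but then adds "The response variable will be change from baseline, and we will use baseline as a covariate". The first description gives three outcome rows per participant. The second leaves two informative rows, because change at Week 0 is always zero.

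On the test itself: "This hypothesis will be tested using the treatment-by-time interaction, followed by contrasts in least squares means".

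The only correlation pattern stated anywhere is in the power section for cognitive symptoms (Tower of London): "We used correlations of 0.50 between all occasions, which is probably a conservative estimate".

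**The concern.** With three visits, AR(1) imposes one common variance and makes the Week 0–8 correlation the square of the correlation between adjacent visits. The variance of the Week 0 to Week 8 change depends directly on that correlation. If AR(1) is wrong and retained, the standard error, confidence interval and p-value of the Week 8 contrast are wrong too.

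The pretest protects only partly. Non-significance does not show that AR(1) fits, and at this sample size the test has limited power against moderate departures. The default therefore sits on the more restrictive side. That would be reasonable if unstructured covariance were expensive to estimate, so the question is what each side costs.

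**Working it through.** **The plan's own figure.** The documents give no figure for the covariance rule. The related figure is primary power: 70 per arm, difference 7, SD 12.5, two-sided 0.05. The noncentrality is 7 / (12.5 × √(2/70)) = 7 / 2.113 = 3.313 on 138 df, which gives 0.90822, as tabulated. At a correlation of 0.50 the SD of change is 12.5 × √(2 × (1 − 0.50)) = 12.5, so the same figure applies to the Week 8 change contrast.

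**Inputs.** From the documents: 70 per arm, SD 12.5, 7 points, Weeks 0, 4 and 8. Assumed: test level 0.05, REML with model-based standard errors, complete data, and all correlations other than 0.50. Correlations are written as 4-week/8-week. Simulations used 3,000 to 20,000 trials per scenario, and ranges below are across repeated runs.

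**Reading A: three visits as outcomes.** Unstructured has 6 parameters and AR(1) has 2, so the test has 4 df. With equal variances, AR(1) settles on the adjacent-visit correlation a and implies a² for Week 0–8, where the truth is b. The Week 8 standard error is then off by the factor √((1 − a²)/(1 − b)):

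| a/b | Factor | AR(1) kept | Rule overall, against unstructured |
|---|---|---|---|
| 0.6/0.5 | √(0.64/0.50) = 1.13 | 47–49% | power 88.7% v 90.5% (repeat run 89.5% v 91.3%) |
| 0.5/0.4 | √(0.75/0.60) = 1.12 | 56% | power 82.5% v 85.1% |
| 0.7/0.4 | √(0.51/0.60) = 0.92 | 63–65% | type I error 6.0–6.4% v 4.9–5.2% |
| 0.5/0.5 | √(0.75/0.50) = 1.22 | 7–9% | power 90.7% v 91.4% |

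In the first two rows, the standard error in trials that keep AR(1) is 9–13% too large; in the third it is 8–9% too small. Type I error within those trials is 2.5–2.7% at 0.6/0.5 and 6.9–7.1% at 0.7/0.4. In the last row the misfit is gross and the test usually catches it.

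**Reading B: change at Weeks 4 and 8, baseline-by-visit covariate.** Unstructured has 3 parameters and AR(1) has 2, so the test has 1 df. The only restriction is equal residual variance at the two visits. Those variances are proportional to 1 − a² and 1 − b², and AR(1) uses their average.
- 0.6/0.5: variances 0.64 and 0.75, average 0.695. The Week 8 factor is √(0.695/0.75) = 0.963. AR(1) is kept in 82% of trials; type I error is 5.7%.
- 0.7/0.4: variances 0.51 and 0.84, average 0.675. The factor is √(0.675/0.84) = 0.896. AR(1) is kept in only about 3.5% of trials, where the standard error is about 13% too small; overall type I error is 4.9–5.1%.
- 0.5/0.4: type I error 5.3%.
- 0.5/0.5: equal variances, so AR(1) is correct. It is kept in 95% of trials; type I error is 4.7%.

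The Week 4 error goes the other way. With raw scores following AR(1) at 0.7, the variances are 0.51 and 0.7599 (average 0.635). If AR(1) is used, the Week 4 standard error is 11.6% too large and the Week 8 one 8.6% too small.

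**Cost of unstructured when AR(1) is exactly true (Reading A).** Week 8 power is 76.5% v 76.6% at adjacent correlation 0.5, and 90.0% v 90.2% at 0.7. The loss is at most 0.2 points.

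**Dropout.** One run was made under Reading A: 100 per arm, 0.50 at all occasions, about 30% lost before Week 4 and an assumed 14% of the rest before Week 8, 700 trials. The test rejected AR(1) in 88%. Week 8 type I error was 4.1% under both the rule and unstructured; for the interaction test it was 5.1% v 5.0%.

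**The case against.** The strongest reply is that the plan is prespecified, compares its default with unstructured covariance, and has a convergence fallback; starting from a parsimonious structure is a recognised approach. Across all scenarios the rule's overall type I error ran from 4.1% to 6.4%, and the conditional rates in trials that keep AR(1) are not the trial's operating characteristics. This stands, and it limits the point to a minor one.

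Four stronger readings are tempting but not supported:
- **That the rule gives wrong standard errors in general.** They are right when AR(1) holds, and gross misfit usually triggers the switch. The exposure is moderate misfit that the test misses.
- **That the plan contradicts itself by assuming 0.50 at all occasions.** That figure is a planning simplification for a secondary endpoint, in a paragraph where the authors say they cannot estimate the covariance parameters. The primary power calculation uses no correlation. At 0.50 throughout, little is lost under either reading.
- **That the squared-correlation restriction drives the primary analysis.** It applies only under Reading A. Under Reading B the effects shrink, and at 0.6/0.5 the Week 8 error changes sign.
- **That the expected 30% dropout makes the rule harmful.** Likelihood methods under missing at random do rely on the covariance model, but no harm was shown. In the one run, dropout was unrelated to the scores, so it does not settle the question either way.

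The hypothesis is tested first by the treatment-by-time interaction, whereas these figures concern the follow-up contrasts. Apart from the dropout run, the effect on the interaction test was not measured.

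**Conclusion.** The point holds as a minor one. Keeping AR(1) unless a test of unstated level rejects it leaves the Week 4 and Week 8 standard errors open to error in either direction when misfit is moderate. With three visits as outcomes, the price is about 2–3 power points or a type I error of about 6% at the assumed correlations. With two change scores, overall type I error is close to that of unstructured. All sizes rest on the assumed 0.05 test level, model-based standard errors, complete data, and correlations that the documents do not supply. The case for change is that the default saves nothing of value: at most six parameters must be estimated from 140 or more participants.

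**What to change.** In General Modeling, prespecify unstructured covariance with Kenward-Roger degrees of freedom for the primary and secondary mixed models, and delete the AR(1) default and the likelihood ratio pretest. Keep simpler structures only for non-convergence, in a fixed order and with robust standard errors. In the Primary Outcome text, state whether the response is the score at three visits or the change at Weeks 4 and 8 with baseline as covariate, so that the matrix is defined.

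The cost is a few sentences of SAP wording. There is no effect on sample size, visits or data collection, and the power given up if AR(1) is in fact true is at most about 0.2 points.

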We propose to conduct a randomized controlled trial (RCT) investigating a novel neurosteroid intervention in Gulf War Veterans with GWVI. Research participants will be recruited via Durham VA IRB-approved local advertising (flyers), Durham VA IRB-approved letters (and follow-up phone calls utilizing a Durham VA IRB-approved phone script), Vet Centers, and the VISN 6 MIRECC Post-Deployment Mental Health Data Repository (over 95% of these Registry participants have provided permission to be re-contacted for future research studies; over a quarter of Veterans in this OEF/OIF/OND era Registry are also Gulf War era Veterans), and by referral from the Durham VA, Raleigh CBOC, Greensboro CBOC, and Morehead City CBOC medical and behavioral health care providers. The target number of participants for this study is 140 subjects who complete at least 4 weeks of the study post-randomization (70 subjects per group, randomized to either adjunctive pregnenolone or placebo). Based on our prior investigations with pregnenolone, we conservatively estimate a drop-out rate of 30%. The power analysis for this study in GWVI was conducted under the assumption that 140 participants reach Visit 4 of the study (i.e. 4 weeks post-randomization). With an estimated 30% drop-out rate, we thus anticipate that we will have to randomize approximately 200 participants to achieve this goal.

Enrolled subjects will be 1). Veterans deployed to the Gulf War theater of operations between 1990 and 1991, 2). Gulf War Veterans who report at least 2 of the following 3 symptoms that began in 1990 or thereafter, that have lasted for more than 6 months, and that are present at the time of screening: a) fatigue that limited usual activity, b) musculoskeletal pain involving 2 or more regions of the body, c) cognitive symptoms (memory, concentration, or attentional difficulties by self-report, 3) on a stable medication regimen (no change in past 4 weeks) and no anticipated change in medications during study, 4) Able to provide informed consent for study participation. Only Gulf War era Veterans will be enrolled into this study. There will be no non-Veteran participants enrolled in this study.

RECRUITMENT PROCEDURES

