Missing data: The mixed models used to evaluate the continuous response variables are able to handle moderate amounts of missing data provided they are missing at random. We will examine the missing at random assumption by assessing differences between dropouts and completers on baseline as well as response variables up to point of premature withdrawal. If the missing at random assumption does not appear to be tenable, we will report the mixed models results but spend additional effort characterizing treatment effect at time of premature withdrawal.

Statistical Computing and Programming: All statistical computing using the current version of SAS.

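### The fallback for mixed-model failure, run as standard repeated-measures ANOVA, would drop participants seen at only one of Visits 4 and 6 and lose the missing-at-random basis (low priority)

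*Combined protocol and SAP*

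**What the plan says.** **Fallback.** The General Modeling paragraph of the Statistical Analysis Plan fits repeated-measures mixed models with AR(1) and unstructured covariance, and chooses between them by likelihood ratio test. It then allows that "it is always possible that these mixed models may fail to converge or encounter difficulties based on their use of asymptotics", in which case "we will move to analyses that assume compound symmetry, and use a Huynh-Feldt correction". It names no procedure for this step and does not say how a participant with a missing visit is treated.

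**Missing data.** The next paragraph says that the mixed models "are able to handle moderate amounts of missing data provided they are missing at random". It adds a comparison of dropouts with completers, and further description of the effect at withdrawal if missing at random looks untenable. Neither supplies an estimation method for the fallback.

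**Visits and response.** Outcomes are "to be administered at Visits 2, 4, and 6; each study visit is two weeks apart", so Visit 4 (Week 4) is the first outcome assessment after randomisation. Under Study Interventions, "The response variable will be change from baseline, and we will use baseline as a covariate", although the same paragraph also lists Weeks 0, 4 and 8 as the within-subject levels.

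**Expected loss.** Subject Recruitment says "we conservatively estimate a drop-out rate of 30" per cent and, on that basis, that "we will have to randomize approximately 200 participants to achieve this goal", the goal being 140 at Visit 4.

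**The concern.** A Huynh-Feldt adjustment belongs to univariate repeated-measures ANOVA. In its standard SAS form (SAS is the stated software), that analysis removes anyone lacking one of the repeated measures. A participant with a valid Week 4 score who leaves before Week 8 would count in the mixed model and vanish from the fallback.

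Two things are at stake. One is the information in those Week 4 scores. The other is the assumption behind the result: a likelihood analysis of all observed visits allows late dropout to depend on the Week 4 outcome, and a completers' analysis does not. The plan itself regards that kind of dropout as worth checking, since it will compare dropouts and completers on responses up to withdrawal. The switch could apply to the primary endpoint and to every secondary endpoint analysed in the same way.

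**Working it through.** **1. The plan's own figures.** Number to randomise: 140 / (1 − 0.30) = 200, as stated. Power at 70 per group for a difference of 7, SD 12.5, two-sided alpha 0.05, by noncentral t: 0.9082, against the tabulated 0.90822. Both reproduce.

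**2. Who the fallback removes.** The power analysis was "conducted under the assumption that 140 participants reach Visit 4 of the study (i.e. 4 weeks post-randomization". So 200 − 140 = 60 are expected to leave before any post-baseline outcome. They have no change score and add no response to the planned mixed model either. If raw scores at three weeks were modelled instead, they would add baseline values only, and almost nothing to the treatment contrast. The loss that belongs to the fallback is therefore participants seen at only one of Visits 4 and 6.

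**3. How many.** Let f be the share of the 140 lost between Visits 4 and 6. The documents do not give f, so it is an assumption. Completers = 140 × (1 − f); extra loss = 140 × f. Power is for 7 points at SD 12.5 on completers alone.

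| f | Completers | Extra loss | Extra loss, % of 200 | Power |
|---|---|---|---|---|
| 0% | 140 | 0 | 0 | 0.908 |
| 5% | 133 | 7 | 3.5 | 0.894 |
| 10% | 126 | 14 | 7 | 0.877 |
| 15% | 119 | 21 | 10.5 | 0.858 |
| 20% | 112 | 28 | 14 | 0.836 |

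The mixed model would lack the same Week 8 values, so only part of the fall in power is due to the fallback.

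Alternative reading: if 30% is total dropout to Week 8 at a constant rate, 200 × √0.70 = 167.3 reach Visit 4 and 200 × 0.70 = 140 complete. The extra loss is 167.3 − 140 = 27.3, or about 27 (27.3 / 200 = 14%).

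**4. Bias.** This was examined by large-sample simulation, with true effect 7, SD 12.5, 10 to 26% late dropout and baseline as covariate. A missing-at-random estimate using all observed visits gave 6.9 to 7.0. Completers gave:

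| Where dropout depends on the Week 4 change | Completers' estimate |
|---|---|
| Placebo arm only | 6.1 to 6.6 |
| Both arms, same rule | about 7.0 |
| Pregnenolone arm only | 7.4 to 7.9 |

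The largest departures are 6.1 − 7 = −0.9 and 7.9 − 7 = +0.9.

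A separate run used correlation 0.5 and a threshold rule. When 40% of participants with a negative Week 4 change and 5% of the others left, in both arms alike, completers gave 6.87 and the likelihood estimate 7.00. When that rule held on pregnenolone only, and on placebo 5% of those with a negative change and 30% of the others left, completers gave 7.86 against 7.03. With no true effect, the same arm-specific rules gave 0.99 against 0.03.

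**5. What the correction buys.** With change scores at Weeks 4 and 8 there are two repeated measures, so epsilon is 1 and the correction does nothing. With three raw-score levels it adjusts the omnibus within-subject tests, not the single-degree-of-freedom Week 4 and Week 8 contrasts.

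**The case against.** **The trigger is remote.** This stands. AR(1) has two covariance parameters and about 140 participants would contribute. In 300 simulated trials with 70 per arm and 20% random loss after Week 4, the AR(1) and unstructured models converged every time. The plan presents failure only as a possibility.

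**Dropping incomplete participants is inferred, not stated.** This stands in part. A mixed model with compound-symmetry covariance would keep them, and the plan names no procedure. But such a model would not normally carry a Huynh-Feldt correction, and the text describes a move away from the mixed models. If a mixed model was intended, the sentence still needs correcting.

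**A reader might infer that the fallback discards 30% or more of those randomised, at least 60 of 200.** The documents do not support that. They place the 30% before Visit 4, and those participants give the planned model no change score either.

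**A reader might also infer that the fallback is valid only if dropout is completely at random.** That is too strong. With baseline as covariate, a completers' analysis stays valid when missingness depends only on arm and baseline. What is lost is protection when dropout depends on the Week 4 outcome. Nor is the direction of bias fixed: a single scenario with outcome-driven dropout on placebo alone shows an understated effect, but the reverse pattern overstates it.

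**Conclusion.** The point holds, at low priority. If the fallback is triggered and run as standard univariate repeated-measures ANOVA, it removes participants seen at only one of Visits 4 and 6 and leaves the analysis without the missing-at-random basis that the plan claims for the mixed models alone.

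The size is 0 to 28 participants for an assumed 0 to 20% loss after Visit 4, or about 27 if the 30% is total dropout to Week 8. Bias is near zero when the same dropout rule acts in both arms. It reached about 0.9 points in either direction, on a true effect of 7, when Week 4 outcomes drove dropout differently by arm. These figures rest on assumed dropout patterns and correlations that the documents do not supply. They illustrate the risk and do not forecast it.

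**What to change.** Delete the Huynh-Feldt step and keep the fallback inside the likelihood-based mixed model, using all observed visits:

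- If the unstructured fit fails, use the AR(1) fit already planned. With two change-score visits, compound symmetry is the same model as AR(1), and heterogeneous Toeplitz the same as unstructured, so a longer list adds nothing. If three raw-score visits are modelled, compound symmetry is a further option.
- Use Kenward-Roger degrees of freedom to deal with the concern about asymptotics. Sandwich standard errors would not, because they are themselves asymptotic.

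The cost is a sentence or two in the General Modeling paragraph, with no change to data collection. The downside is that a simpler covariance may be misspecified, which can itself bias the estimate when data are missing at random. The unstructured fit should therefore be reported as a sensitivity analysis wherever it converges.

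### Comparing dropouts with completers cannot show whether data are missing at random, yet it alone triggers further work, and no specified analysis departs from that assumption

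*Combined protocol and SAP*

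**What the plan says.** The Missing data paragraph makes the mixed models' validity conditional on MAR and then gives one way of judging that condition: "We will examine the missing at random assumption by assessing differences between dropouts and completers on baseline as well as response variables", the responses being those seen before withdrawal. No test or threshold is stated. If the assumption looks doubtful, "we will report the mixed models results but spend additional effort characterizing treatment effect at time of premature withdrawal". Neither the rest of the Statistical Analysis Plan nor the analysis text under Study Interventions specifies an analysis that relaxes MAR. The fallbacks under General Modeling concern covariance structure and convergence.

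On the amount of loss, Subject Recruitment says "we conservatively estimate a drop-out rate of 30" percent, and "The power analysis for this study in GWVI was conducted under the assumption that 140 participants reach Visit 4 of the study". Study Timeline item 9 schedules the SF-36 at Visits 2, 4 and 6, so Visit 4 is the first post-baseline measurement. The visit after early withdrawal (Follow-up Plans) does not list the SF-36. That list also leaves out the EKG sought elsewhere, and the Schedule of Events is not in the available text. This therefore shows only that the SF-36 is not listed there, not that it would not be done.

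On the model, Study Interventions says "The response variable will be change from baseline, and we will use baseline as a covariate", but also describes "one within subjects factor with three levels (Weeks 0, 4, 8 of treatment post-randomization"). The contrasts are set out so: "These contrasts will examine the difference between the treatments at Weeks 4 and 8"; neither week is named as primary.

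**The concern.** A difference between dropouts and completers on observed scores is evidence against missing *completely* at random. It is compatible with MAR, under which the mixed model remains valid. Finding no difference does not support MAR, because MAR fails when dropout depends on unobserved values after conditioning on the observed ones.

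For anyone lost before Visit 4, the SF-36 part of the check is the baseline score alone. If the change score is the response, these participants supply no response. If Week 0 is a response level, they enter the model with a baseline only. Both readings rely on MAR for their later scores. The fallback, an effect at the time of withdrawal, has no post-baseline SF-36 behind it for them.

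At stake is the between-arm contrast on the primary endpoint. As written, a reader could not learn how different the unseen scores would have to be between arms to change the conclusion.

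**Working it through.** **The plan's own figures.** 140 / (1 − 0.30) = 200 randomised, and 200 − 140 = 60 without Visit 4 data, about 30 per arm of 100. A two-sided t-test with 70 per group, difference 7 and SD 12.5 gives power 0.908 (noncentral t), as in the plan's table.

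**A fixed shift in the dropouts.** Suppose 30% of each arm leaves at random, and the unseen changes of drug-arm dropouts are worse by 7 points than MAR predicts. The effect over all randomised participants is 7 + 0.30 × (−7) = 4.9. In 4,000 simulated trials (100 per arm) the baseline-adjusted model returned 7.01 against a true 4.86. The baseline comparison was significant in 5.4% of trials, which is the chance rate. With dropout driven by baseline instead (MAR), the comparison was significant in 96% of trials and the estimate was 7.03 against a true 7.02.

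**A dropout model.** Assumptions: 100 per arm; scores at Weeks 0, 4 and 8 with SD 12.5 and equal correlations r of 0.3 to 0.7; true effects 3.5 at Week 4 and 7 at Week 8. Worse scores raise dropout through a logistic model with slope 0.3 to 1.0 per SD. Loss is 30% per arm, all before Visit 4. The estimate is the arm effect from a regression on baseline and arm in those observed. The flag is p < 0.05 on one t-test of baseline SF-36. Week 8 is this review's choice of main contrast.

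| Dropout mechanism | Flagged | Week 8 estimate (true 7) |
|---|---|---|
| Baseline-driven, both arms (MAR) | 48% to 100% | 6.9 to 7.0 |
| Drug arm driven by the part of Week 8 that baseline does not predict; placebo random | 4% to 6% | 7.8 to 10 |
| The same in placebo only; drug random | about 5% | 4.0 to 6.2 |
| Both arms, placebo slope half the drug slope | about 5% | 7.4 to 8.4 |
| Both arms, equal slopes | about 5% | within 0.1 of 7 |
| Drug arm driven by the raw Week 8 score | chance rate to nearly half | 7.6 to 9.9 |

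With no true effect, the false-positive rate (nominal 5%) is about 8% to 34% in the second row and 5% to 11% in the fourth. With less loss, the second row gives 7.5 to 9.1 at 20% and 7.2 to 8.1 at 10%. Testing the 11 scales listed at Visit 2 (pairwise correlation 0.5 assumed) flags completely random dropout in 29% to 32% of trials. The second row is flagged equally often, so more scales add only chance flags. Treating Week 0 as a response level changes estimates by less than 0.1.

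**Tipping point.** Let δ be the number of points by which drug-arm dropouts fall below their MAR prediction. The contrast D loses significance where

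D − 0.30δ = 1.96 × √(SE² + δ² × 0.3 × 0.7 / 100), with SE = 12.5 × √(1 − r²) × √(2/70).

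SE is 2.02, 1.83 and 1.51 at r = 0.3, 0.5 and 0.7. For D = 7 and r = 0.5, δ = 10.9: the left side is 7 − 3.3 = 3.7 and the right side is 1.96 × √(3.35 + 0.25) = 3.7. Over r = 0.3 to 0.7:

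- D = 7: δ from 9.8 to 12.8
- D = 5: δ from 3.5 to 6.6
- D = 4: δ from 0.2 to 3.4

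**The case against.** The strongest reply is that the plan loses little. A false alarm costs almost nothing, since the mixed model is reported anyway and the extra work only adds to it. This stands: the harm lies in the missed case.

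Second, the simulation is hard on the check. With all loss before Visit 4, no post-baseline response enters the comparison, whereas participants lost later would contribute Week 4 scores. That is fair as to the flag rates. But Week 4 scores are observed data too, so the logical gap remains, and loss before Visit 4 is how the plan itself sizes the trial. The plan calls its 30% conservative, and smaller loss shrinks the bias.

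Third, the mechanisms are invented. Nothing in the documents establishes dropout that depends on unseen outcomes differently by arm, and equal mechanisms leave the estimate essentially unbiased. An estimate of 7 would need a shift of about 10 to 13 points, 0.8 to 1 SD, to lose significance. All this stands, and it limits what can be said about size. It does not rescue the check, and a smaller estimate is much more fragile.

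**Conclusion.** The concern holds. The stated check cannot decide the assumption it is meant to examine, the only further step depends on it and has no method, and no specified analysis departs from MAR. This follows from the plan's wording and needs no simulation.

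The exposure, about 60 of 200 participants without a post-baseline SF-36, follows from the plan's own loss figure and visit schedule. The size of any bias in this trial is unknown, as is its direction: across the assumed mechanisms a true 7 was estimated anywhere from 4.0 to 10. These figures show what the check can miss; they are not a forecast. The mixed model itself is not faulted as the primary analysis.

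**What to change.** Keep the dropout-versus-completer comparison as a description of who leaves. Remove its role as a check of MAR and as a trigger.

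Prespecify at least one sensitivity analysis that departs from MAR for the SF-36 Physical Component contrast at Week 8, and at Week 4 if that also supports the conclusion. Run it whatever the comparison shows, and include every randomised participant with a baseline score. One suitable choice is multiple imputation with a shift δ varied separately in each arm, since bias arises when the arms differ, reporting the δ at which the conclusion changes. Each point of δ in one arm moves the contrast by about 0.3 points at 30% loss, 0.2 at 20% and 0.1 at 10%. An equivalent method that departs from MAR would also do.

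The cost is SAP wording and modest SAS programming on data already collected, with no change to visits or to the primary model. The drawback is that the result may have to be reported as less robust.
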